### **8.2.3 Premature Subject Withdrawal**

All subjects are free to withdraw from participation in the study at any time, for any reason, specified or unspecified, and without prejudice to further treatment. The criteria for enrollment are to be followed explicitly and if a subject who does not meet enrollment criteria is inadvertently enrolled, that subject should be withdrawn from the study and the Sponsor or CRO must be notified.

Subjects should not be asked to withdraw from the study because of experiencing AE, lack of efficacy, pregnancy, or lack of compliance to the clinical study protocol, etc. Those patients can stop their study treatments (for subjects who do not comply the protocol specified instructions and procedures, every effort will be made to keep them in the study after stopping treatment unless there is an adverse impact on subject safety). Discontinuation from study treatment does not automatically lead to a complete withdrawal from the study. Subjects discontinuing from study treatment are strongly encouraged to continue in the study up to the study completion (Follow-up Phone Visit, Week 13).

Subjects who decide they do not wish to remain in the study should NOT be considered withdrawn from the study UNLESS they withdraw their consent. Subjects are encouraged to return to all scheduled site and telephone visits, perform all procedures (including eDiary completion and blood draws) and follow the all requirements of the protocol (including the prohibited therapies), but without study treatment administration, until the end of the study (Follow-up Phone Visit, Week 13).

The reason for study treatment discontinuation and withdrawal from the study will be separately recorded. When the subject discontinues study treatment and/or withdraw from the study, the reason will be recorded in the medical records and eCRF using the below categories for discontinuation of study treatment and withdrawal from the study respectively.

The reasons will be grouped into three main categories: “study treatment related”, “not study treatment related”, and “uncertain” and more specific sub-categories will be described under each of the three main categories.

- Study treatment related
  - Lack of efficacy
  - Adverse events
  - Deviation from protocol (Please specify the deviation)
  - Other
- Not study treatment related
  - Adverse events
  - Prohibited Medication Use
  - Pregnancy
  - Deviation from protocol (Please specify the deviation)
  - COVID-19
  - Subject does not meet enrollment criteria and inadvertently enrolled
  - Other
- Uncertain
  - Lost to follow up
  - Withdrawal of informed consent by subject without reason
  - Other

In all cases, the reason for discontinuation of study treatment or withdrawal from the study must be recorded in the eCRF and if the reason is not known, the investigator must make every effort to confirm the reason.

If a subject is withdrawn early from the study, the following procedures will be performed:

- Subjects will have Early Termination (ET) procedures performed as shown in the Schedule of Events (see **Section 10.2**).
- All ET procedures should be completed and recorded on the ET eCRF page. If withdrawal occurs at a regular scheduled visit, the Early Withdrawal eCRF page should be used instead of the regular visit eCRF page to record any information related to the visit.

It is important to evaluate these subjects at the study center as soon as possible. Investigators must make at least 3 documented attempts to contact subjects who fail to attend scheduled visits by telephone or any other means and document the attempts. After 3 documented unsuccessful contact attempts the subject can be considered lost to follow-up.

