#### **10.1.5 Early Termination Visit (if applicable)**

Subjects who are discontinued prematurely from study for any reason after Baseline (Visit 3) must complete the Early Termination Visit. If the subject comes for an Unscheduled Visit and a decision to withdraw the subject is made, then the Early Termination Visit procedures will be performed and the Early Termination Visit eCRF will be completed (and not the Unscheduled Visit eCRF).

During this visit the following assessments and procedures will be performed:

1. Perform physical examination.
2. Obtain vital signs measurements.

3. Obtain subject's weight.
4. Obtain blood and urine samples for laboratory testing.
5. Perform a urine pregnancy test.
6. Perform a 12-lead ECG.
7. Administer the WOMAC questionnaire for the target knee.
8. Perform PGA.
9. Perform PGIC.
10. Perform a QOL Questionnaire.
11. Remove the patch on a skin.
12. Instruct a subject to perform the following assessments in the eDiary when they remove the patch at the site:
  - a. Perform and record scoring of the pain of the target knee using the NRS 11-point pain scale
  - b. Record the time of patch removal.
  - c. Record the time of not scheduled complete patch detachment and the reason (if applicable).
  - d. Record the number of tablets of rescue medication used, the time and the reason.
13. Review the subjects' eDiary entries.
14. Collection of unused study drug and rescue medication.
15. Review subject's use of rescue and concomitant medications.
16. Perform drug accountability/reconciliation of study drug and rescue medication. The reconciliation (missing patch, failure of application, unscheduled detachment and application, etc.) will be recorded in the eCRF.
17. Perform dermal safety assessment (irritation, discomfort, and adhesion).
18. Review AEs. The irritation and discomfort reported in the eDiary will be treated as AEs.
19. Record the date and the reason of early termination in the eCRF.

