#### **13.3. Analysis Populations**

The following analysis populations are planned for this study:

- Intent-to-Treat (ITT): Includes all consented and randomized subjects. Regardless of any protocol deviations and/or treatment compliance, analyses performed on the ITT set will be based on the randomized treatment assignment and all available data. The ITT will be used as the primary set for analysis of efficacy endpoints.
- Safety Analysis Set (SAF): Includes all subjects who have had at least 1 patch of double-blind study drug applied and who have at least 1 post-dose safety measurement during the Double-blind Treatment Phase. In the unlikely event that errors may have occurred in treatment arm assignments, then analyses using the SAF will be based on treatment actually received. The SAF will be used for the analysis of dermal evaluations and safety endpoints.

Inclusion in the analysis populations will be determined prior to database lock.

If a subject is randomized incorrectly or is administered the incorrect study drug, analyses of the ITT population will be based on the assigned treatment whereas all other analyses will be based on the actual treatment.

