5.1 INTENT-TO-TREAT SET[ITT]

Intent-to-treat (ITT) analysis set includes all consented and randomized subjects. Regardless of any protocol deviations and/or treatment compliance, analyses performed on the ITT set will be based on the randomized treatment assignment and all available data. The ITT set will be used as the primary set for analysis of primary and secondary efficacy endpoints. If a subject is randomized incorrectly or is administered the incorrect study drug, analyses of the ITT set will be based on the assigned treatment whereas all analyses of the safety analysis set will be based on the actual treatment.

Noven Pharmaceuticals, Inc.

Protocol HP-5000-US-07

Statistical Analysis Plan

Page 17 of 58

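### Protocol 8.2.3 ends follow-up for inadvertently enrolled subjects who remain in ITT, which creates avoidable missing Week 12 scores

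*Protocol*

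**What the plan says.** Protocol 8.2.3 (Premature Subject Withdrawal) opens with a rule for subjects who turn out not to meet the entry criteria: "that subject should be withdrawn from the study and the Sponsor or CRO must be notified". The paragraphs that follow set a different policy. Adverse events, lack of efficacy, pregnancy and non-compliance are not grounds for asking a subject to leave, and "Discontinuation from study treatment does not automatically lead to a complete withdrawal from the study". Those subjects are encouraged to attend every visit off treatment up to the Week 13 call.

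The section's list of reasons includes "Subject does not meet enrollment criteria and inadvertently enrolled", under the category of reasons not related to study treatment. For anyone withdrawn early, "Subjects will have Early Termination (ET) procedures performed as shown in the Schedule of Events", and the ET visit in Protocol 10.1.5 includes "Administer the WOMAC questionnaire for the target knee".

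The primary analysis set makes no exception for ineligibility. Protocol 13.3 has "Intent-to-Treat (ITT): Includes all consented and randomized subjects" and adds "Regardless of any protocol deviations and/or treatment compliance, analyses performed on the ITT set will be based on the randomized treatment assignment". SAP 5.1 repeats this and bases the analysis on all available data. SAP 9.1 plans a count of subjects enrolled in error, by arm and overall. Protocol 8.3 does not replace a subject who withdraws after randomisation and the first patch.

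**The concern.** The plan counts an ineligible randomised subject in its primary analysis and also instructs the site to stop following that subject. The resulting gap in the data comes from the protocol's own rule, not from the subject's choice.

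The two rules in 8.2.3 can also fall on one person. Exclusion criterion 3 covers breaches of the washout restrictions, including rescue use in the 3 calendar days before Baseline. If a breach is found after randomisation, the subject is ineligible, so the first paragraph says withdraw. The subject can also be read as non-compliant, so the second paragraph says do not ask for withdrawal and make every effort to retain. A site cannot follow both.

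At stake is how far the Week 12 comparison in ITT rests on an untestable assumption for subjects whose scores could have been collected.

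**Working it through.** **Following one subject through the documents**

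1. Ineligibility is found after randomisation. Protocol 8.2.3 sends the subject out of the study after an ET visit.
2. Scores before withdrawal are kept. The ET WOMAC is assigned by SAP 6.3, Table A: days 1–10 to Week 1, 11–17 to Week 2, 18–38 to Week 4, 39–73 to Week 8, and 74 or later to Week 12. An ET visit on day 20 can supply Week 4 only; Weeks 8 and 12 are then missing.
3. The subject stays in ITT (Protocol 13.3, SAP 5.1).
4. The reason is coded as not related to study treatment. The discontinuation intercurrent event covers treatment-related reasons only (Protocol 13.4.3.1, SAP 16.1.4), so the zero-benefit rule does not apply. Later scores are left to the MAR assumption of the MMRM (SAP 16.1.2).
5. Sensitivity analyses: Protocol 13.4.3.1 holds reasons that are not treatment-related, or uncertain, at MAR. SAP 16.1.5 has three scenarios. Those for lack of efficacy, and for lack of efficacy plus adverse events, leave this subject at MAR. Only the scenario that treats all dropout as MNAR changes the assumption.

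No other section continues these subjects' scheduled assessments.

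**Scale (illustrative)**

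The plan states 80% power at two-sided 0.05 (Protocol 13.2). This cannot be reproduced because the effect size and sample size are redacted. No rate of inadvertent enrolment is given either. Assumed: standardised effects δ from 0.20 to 0.40, 1:1 allocation, and a share d of randomised subjects affected.

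- n per arm = 2(1.960 + 0.842)²/δ², rounded up: 393 at 0.20, 175 at 0.30, 99 at 0.40.
- Power = Φ(δ√(n/2) − 1.960). At δ = 0.30: 0.30 × √87.5 = 2.806, less 1.960 is 0.846, giving 80.1%.
- (a) The share d contributes no information: replace n by n(1 − d). At d = 5%: 0.30 × √83.125 = 2.735, less 1.960 is 0.775, giving 78.1%.
- (b) The share d is followed, its scores enter the analysis and its true effect is zero: replace δ by δ(1 − d). At d = 5%: 0.285 × √87.5 = 2.666, less 1.960 is 0.706, giving 76.0%.

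| d (assumed) | (a) power, δ 0.20–0.40 | (b) power, δ 0.20–0.40 |
|---|---|---|
| 1% | 79.7–80.0% | 79.3–79.6% |
| 2% | 79.3–79.6% | 78.5–78.8% |
| 5% | 78.0–78.3% | 75.9–76.2% |
| 10% | 75.8–76.1% | 71.3–71.7% |

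Column (a) overstates the loss, because the MMRM uses scores from before withdrawal. Column (b) is lower than (a) throughout. At 5%, an effect of 0.30 would be seen as 0.285 if the scores were observed, while MAR handling would not show that reduction.

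**The case against.** The strongest reply is that the sentence is a deliberate exception. The retention paragraph does not name ineligibility, the sentence was kept when the retention policy was written around it, and ineligibility has its own reason code. Late discoveries should also be uncommon, since eligibility is checked at Visits 1, 2 and 3 and recorded in the IWRS before randomisation. Ineligibility usually reflects facts fixed before randomisation in a blinded trial, which makes MAR more plausible than for most dropout. Continued participation would also hold ineligible subjects to the protocol's restrictions.

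Much of this stands: the number is probably small, MAR is plausible, and the burden is real. Three things do not follow. An intended exception would still conflict with an ITT set that needs these subjects' outcomes. The reason code settles nothing, because the same list serves both treatment discontinuation and study withdrawal. And 8.2.3 does not require ineligibility to rest on pre-randomisation facts, so something seen during treatment could prompt removal.

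A further limit is that Protocol 13.4.3.1 and SAP 16.1.4 drop WOMAC scores taken more than 24 hours after patch removal. Read literally, scores from a retained subject who is off the patch would not enter the primary analysis. They would enter the supplementary analysis without intercurrent-event adjustment (SAP 16.1.6).

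A reader might also infer that these subjects are excluded after randomisation, that their outcomes are lost altogether, or that the rule matters because it costs power. The documents support none of these. ITT retains the subjects. Earlier scores and an ET WOMAC are collected and windowed. Following them off treatment could lower power further, as column (b) shows.

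**Conclusion.** The point holds as an inconsistency that produces avoidable missing data in the primary analysis set. For an inadvertently enrolled subject, scheduled WOMAC collection ends with the ET visit, Week 12 is missing unless that visit is on day 74 or later, and MAR fills the gap in the primary model and in the Protocol's sensitivity analyses. The SAP's all-dropout MNAR scenario tests the assumption in part but cannot recover scores that were never collected.

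The size is unknown. Under the assumed rates, the information loss is under 1 power point at 1–2%, about 2 points at 5% and about 4 at 10%. These figures rest on assumed effect sizes and rates, and they are not the reason to act. The reason is that the dependence on MAR can be reduced cheaply. It is a worthwhile clarification rather than a threat to the trial's conclusion.

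**What to change.** Reconcile the first paragraph of Protocol 8.2.3 with the retention text in the same section and with the ITT definition. Separate two matters that the sentence joins: what happens to study treatment, which is for the sponsor to settle and is not prescribed here, and whether outcomes are collected. On the second, state that scheduled efficacy assessments through Week 12 continue for every randomised subject unless consent is withdrawn or safety prevents it. Say which rule governs a subject who is both ineligible and non-compliant, such as a washout breach found late.

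In the SAP, state whether the 24-hour patch-removal rule applies to retained subjects who are permanently off the patch, so that it is clear which analyses use their scores. Keep the all-dropout MNAR scenario for subjects who are still lost.

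The cost is a short protocol amendment with the approvals in Protocol 14.6 and 15.3, a clarifying sentence in the SAP, visit burden for a few ineligible subjects, and possibly a slightly smaller observed ITT effect wherever their scores are used.

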### **8.3. Subject Replacement Criteria**

Subjects who withdraw after randomization and the application of the first treatment patch will not be replaced.

## 9. TREATMENTS

### 9.1. Identification of Investigational Product

The following is a description of study drug:

- HP-5000 [REDACTED] patch  
Each patch contains [REDACTED] diclofenac sodium.

HP-5000 will be supplied as diclofenac sodium in a patch manufactured by [REDACTED]  
[REDACTED]

#### 9.1.1 Labeling

Labels will be computer-generated for all investigational products (IPs) with the following information (other information may also be included as needed):

- Protocol number
- Subject number (record at the time of dispensing)
- Package contents (quantity)
- Storage instructions
- Caution: “New Drug – Limited by United States Law to Investigational Use” and “Keep out of reach of children”
- Sponsor name and address

#### 9.1.2 Packaging

In the Double-blind Treatment Phase, HP-5000 and placebo patches will be packaged so as to be blinded to the investigator, the study clinic personnel, and the subjects.

Sites and subjects will be instructed to save all empty packaging or packaging containing unused patches for final disposition by the Sponsor or its designee.

The Drug Dispensing Log must be available for monitoring, auditing, or inspection. [Section 9.8](#) details the accountability of clinical supplies through the use of a Drug Dispensing Log.

### 9.2. Treatments Administered

HP-5000 will be administered [REDACTED] for 12 weeks.

The treatment arms for this study are the following:

[figure not shown]
**Table 1 Treatment Arms**

Treatment Arm	Treatment
HP-5000	HP-5000 [REDACTED] patch Each patch contains [REDACTED] diclofenac sodium.
Placebo	HP-5000 [REDACTED] Placebo patch Each patch contains 0% [REDACTED] diclofenac sodium.

One patch (100 cm^2) will be applied [REDACTED] to alternate sides (inner and outer knee) of the target knee after showering/bathing.

Note:

- Subjects will be instructed not to bathe or shower while wearing the patch.
- In case the patch completely detaches within 24 hours of application, the detached patch will be applied again on the same site. If the detached patch does not re-adhere, a replacement patch (new patch) will be applied on the same site until the next scheduled replacement of the patch (see following sample scheme).

Even if the applied replacement patch completely detaches by accident again, an additional application of another new patch will not be allowed and the subject will wait to apply a patch until the next scheduled replacement.

- Subjects will not be allowed to apply any patches to the non-target knee at any time during the study.
- Even if there is a day when subjects do not take a shower or bath, they need to replace a patch [REDACTED]

Detailed application instructions for subjects will be provided in a separate manual/guide.

### **9.3. Dispensing and Storage**

Study drug supplied by [REDACTED] is to be used exclusively according to this protocol. The investigator is responsible for dispensing study drug according to the dosage and administration scheme and for ensuring proper storage of study drug.

The investigator, or designee, must confirm the receipt of study drug with his/her signature. A copy of this receipt must be kept by the investigator. Until study drug is dispensed to the subjects, it must be stored between 15°C to 30°C (59°F to 86°F) and in a dry place in a securely locked area that is not generally accessible.

All study drug supplies must be stored in a secure locked area with access limited to the investigator or those persons authorized by the investigator to dispense the study drug to subjects. Study drug should be stored as per the label.

### **9.4. Method of Assigning Subjects to Treatment Groups**

In this parallel-group randomized study, subjects who will meet study entry criteria will be randomly assigned in a 1:1 ratio to receive HP-5000 or placebo patches. The randomization numbers will be assigned sequentially through a central interactive web response system (IWRS) as subjects who met eligibility criteria are enrolled into the study. The study center will not be a blocking factor in the randomization schedule. At each visit, subjects will be given a kit containing sufficient study drug to last until the next scheduled study visit.

The randomization schedule will be prepared before the start of the study. No one involved in the clinical conduct will have access to the randomization schedule before the official unblinding of treatment assignment. No subject will be randomized into this study more than once.

### **9.5. Blinding and Unblinding Treatment Assignment**

To protect the blind, placebo patches will be identical in appearance to the HP-5000 patches.

All subjects, investigators, and study personnel involved in the conduct of the study, including the project study team and data management, will be blinded to study drug treatment assignment with the exception of a prespecified unblinded statistician/programmer, who will have access to the randomization code. The unblinded study personnel will not participate in study procedures or data analysis prior to unblinding of the study data to all study related personnel. If an interim analysis is to be conducted, unblinded personnel who are not otherwise involved in the study will prepare the data for review.

Study personnel will endeavor to safeguard the integrity of the study blind to minimize bias in the conduct of the clinical study. Treatment unblinding is discouraged if knowledge of the treatment assignment will not materially change the planned management of a medical emergency. Unblinding will be only permitted in a medical emergency that requires immediate knowledge of the subject's treatment assignment.

In the case of a medical emergency, to appropriately treat the subject, study drug will need to be unblinded. Instructions for breaking the blind will be included in the IWRS manual. The investigator may break the randomization code for an individual subject. However, the investigator should make every effort to discuss the unblinding of the subject with the Medical Monitor prior to unblinding.

If the investigator is not able to discuss treatment unblinding in advance, then he/she must notify the Medical Monitor immediately of the blind breaking incident without revealing the subject's treatment assignment.

In all such cases, the AE necessitating the emergency blind break will be handled as an SAE in accordance with the procedures indicated above. Any broken code will be clearly justified, explained by a comment on the appropriate eCRF page along with the date and reason for study discontinuation; and captured on the SAE Form (see **Section 11.2.6.1** for SAE reporting to sponsor).

The investigator or designee must record the date and reason for unblinding or study discontinuation on the appropriate eCRF for that subject.

If treatment assignment is unblinded for an individual subject, study personnel will be notified of that subject's treatment assignment without unblinding the treatment assignments for the remaining subjects in the study. Thus, the overall study blind will not be compromised. If a subject's treatment assignment is unblinded, he/she may or may not be asked to withdraw from the study. The investigator will make this decision after consultation with the Medical Monitor.

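### Protocol Section 9.5 has study personnel told an unblinded subject's treatment with no need-to-know limit, at odds with its aim of keeping that assignment from the Medical Monitor

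*Protocol*

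**What the plan says.** Protocol Section 9.5 sets the general rule first: "All subjects, investigators, and study personnel involved in the conduct of the study, including the project study team and data management, will be blinded" to treatment, apart from a prespecified unblinded statistician or programmer. A code may be broken only in a medical emergency that needs the assignment at once, and the investigator should try to speak to the Medical Monitor first. The next rule carries a condition, "If the investigator is not able to discuss treatment unblinding in advance", and in that case "he/she must notify the Medical Monitor immediately of the blind breaking incident without revealing the subject's treatment assignment". The date and reason are recorded on the eCRF.

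The closing paragraph of the section then says: "If treatment assignment is unblinded for an individual subject, study personnel will be notified of that subject's treatment assignment". The only limit it adds is that the other subjects' assignments stay blinded. From this it concludes that the overall blind is preserved. Of the unblinded subject it says "he/she may or may not be asked to withdraw from the study", and adds: "The investigator will make this decision after consultation with the Medical Monitor".

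The SAP has no rule for subjects whose code was broken. Unblinding is not among the intercurrent events in SAP Sections 2.4 and 16.1.5.

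**The concern.** One instruction contains knowledge of a broken code and the other spreads it. As written, a Medical Monitor could be kept blind while data management and site raters are told the arm. The section's reassurance concerns the other subjects only and does nothing for the data still to come from the subject whose code was broken.

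Those data include judgements by staff. Irritation and adhesion are scored by an investigator or designee. AEs are classed by relationship to study drug. A discontinuation is classed as related to study treatment, not related, or uncertain, and only the first class triggers the zero-benefit handling in the primary analysis (Protocol Section 13.4.3.1, SAP Section 16.1.4). A rater who knows the arm may lean one way on any of these.

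**Working it through.** The documents give no figure that depends on this point, so the check is mainly a comparison of passages. A rough bound on size follows.

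1. **Who is told.** The notification sentence in Section 9.5 says study personnel and stops there. The same section's general rule uses that term for people involved in conducting the study, including the project study team and data management. Nothing in the protocol or SAP narrows it for the notification.

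2. **Whether the two instructions conflict.** The non-disclosure rule has one recipient, the Medical Monitor, and one condition, no advance discussion. If the Medical Monitor is study personnel, the rules cannot both be followed when that condition holds. If not, both can be followed, but one restricts the assignment and the other circulates it. The Medical Monitor is also consulted on whether the subject stays, so sites need to know which rule applies.

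3. **Whether data still accrue.** They do, because the subject may remain. If patches continue, irritation and adhesion continue to be scored at clinic visits (Protocol Sections 10.3.2.4.1 and 10.3.2.4.2). If patches stop, Section 8.2.3 encourages follow-up to Week 13 without study treatment, and no later adhesion rating arises.

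4. **Which judgements the sentence itself exposes.**
   - *Irritation and adhesion:* exposed when the rater is a designee who would otherwise not have seen the code.
   - *Discomfort:* largely outside the concern, since the evaluator asks the subject to grade it (Section 10.3.2.4.3).
   - *AE causality:* the investigator's assessment (Section 11.2.2.5). The sentence adds only whatever input other staff have.
   - *Discontinuation class:* the investigator must try to confirm an unknown reason (Section 8.2.3). Again the sentence adds only other staff's input.

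5. **Whether any stated process needs wide disclosure.** None was found. Section 9.5 asks for date and reason. The serious adverse event report in Section 11.2.6.1 asks whether and when the investigator was unblinded, not which arm.

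6. **Size.** The documents do not give the expected number of code breaks, so assume 0 to 1% of randomised subjects. In a 1:1 trial the extreme case puts all of them in one arm, which is 2 × 1% = 2% of that arm. Suppose knowledge of the arm changed the discontinuation class for every one of them, and each change moved that subject's WOMAC pain result by 4 points, the largest shift applied in the placebo group in SAP Appendix 3. As an approximation, the arm mean would move by 0.02 × 4 = 0.08 points on the 0 to 20 scale. The range is therefore 0 to 0.08. The part due to the notification sentence is smaller still, by step 4.

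**The case against.** The strongest reply is that little of the harm comes from this sentence. The investigator who breaks the code knows the arm whatever is said to others, and that person assesses causality and is responsible for establishing the discontinuation reason. This stands, and it confines the point to other raters and to project and data staff.

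The scope of study personnel is also partly inferred. Section 9.5 lists investigators separately and applies the term to the unblinded statistician or programmer as well, and Section 9.9 applies it to staff who count patches. The IWRS manual, which holds the code-break instructions and is not available here, may name recipients. That is a fair caution, but the protocol text sets no limit of its own.

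The endpoints are well protected too. WOMAC is completed by the subject, and safety summaries are descriptive, with no formal inference unless otherwise noted (Protocol Section 13.4.4). This also stands.

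A reader might infer that the people told the assignment could influence the blinded data review that settles the analysis sets. The documents do not support this. SAP Section 5 does not say who takes part, and the sets leave almost no room for judgement: ITT is everyone consented and randomised, and the safety set needs one patch applied and one post-dose safety measurement.

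**Conclusion.** The point holds in a limited form. Section 9.5 is inconsistent in aim, and its notification sentence unblinds staff to a subject who may stay in the study, for no purpose the documents state. What is exposed is that subject's later irritation and adhesion ratings while patches continue, and any contribution by the notified staff to AE causality or the discontinuation class.

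Two stronger readings are tempting. One is that the section flatly contradicts itself. That would require the Medical Monitor to count as study personnel, which is not stated, and the non-disclosure rule applies only without advance discussion. The other is that the primary result is at risk. It is not: the effect on WOMAC is negligible, at most 0.08 points under the assumed 0 to 1% and the extreme case above.

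The conclusion rests on code breaks being few, as the emergency-only rule suggests, and on the IWRS manual not already restricting who is told. It is worth correcting because the change is cheap.

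**What to change.** Reconcile the two instructions in Section 9.5 by replacing the notification sentence with: *Study personnel will be informed that the blind was broken, with the date and reason, but not the treatment assignment, which is limited to the investigator, those treating the emergency, and any safety-reporting role the sponsor names as needing it.* Check that the IWRS manual says the same.

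Optionally, where an existing site rater has not seen the code, have that person make the subject's later dermal ratings and classifications. This is the only part that reaches judgements the unblinded investigator would otherwise make.

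The cost is one protocol sentence and a consistency check, with no new staff. Emergency access to the code is unchanged. The small downside is that other site staff no longer learn the arm routinely, but the investigator can still share it when care requires.
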